1.2 SCHEMATIC OF STUDY DESIGN

An overview of the study design is provided in [Figure 1](#) and [Figure 2](#).

Figure 1 Overview of *Original* Study Design

[figure not shown]
[figure not shown]

Figure 2 Overview of Study Design After Stopping Recruitment into the RO7121661 Arm

^a It is planned to stop enrollment when approximately [REDACTED] participants have been recruited in the RO7247669 and nivolumab arms. Patients already included in the RO7121661 arm will remain in the study. The estimated amount of participants enrolled in the RO7121661 arm at the time of recruitment stop will be added to the planned [REDACTED]. The study will not be unblinded.

1.3 SCHEDULE OF ACTIVITIES

The schedule of activities are provided in [Table 1](#), [Table 2](#), and [Table 3](#).

Table 1 Schedule of Activities

Protocol Section	Cycle length 14 days	Screening	On dosing days of all treatment Cycles ^a	Cycle 1 - 5 Day 8	Treatment Discontinuation	Follow-up	In case of Grade ≥2 IRR, suspected anaphylaxis, or Grade ≥ 2 suspected imAEs	
	Day (D)	D -28 to D -1 (unless otherwise indicated)	Every 14 Days (-1/+3 days)	(± 1 day)	≤ 30 Days after Last Dose	90 (±7 days) post last dose, then every 3 months (±2 weeks)	At the time of event	≥48 hours after the onset of an IRR
Screening Assessments								
	Informed consent (incl. RBR)	x						
8.2.8	Medical history and demography	x						
8.2.5	Royal Marsden Risk Score	x						
IMP Administration								
6.1	Study drug administration		x					
Clinical Assessments								
6.5	Previous and concomitant treatments	continuous					x	x
8.3	Adverse events					x	x	x
8.2.1	Physical examination	x	x		x		Weight only	
8.2.1	Height	x						
8.2.2	Vital signs ^b	x	x		x			
8.2.3	12-lead ECG	x	x		x		x	
8.2.4	ECOG performance status	x	x		x			
8.2.6	TTE or MUGA	x						
8.1.2	PRO-assessments	Refer to the PRO assessments table for specific Timepoint Details						
8.8.2	Nutritional assessment (optional)		C1, C4 and upon occurrence of colitis					
8.1.1	Tumor assessment (CT scan of chest, abdomen, pelvis, brain, and other regions as clinically indicated)							
8.11.4	Post-study survival and anti-cancer therapies					x		
Local Laboratory Assessments								
8.2.7 and Appendix 4	Viral serology	x						
	Quantitative immunoglobulins	x						
	Hematology	x	x		x		x	
	Blood chemistry	x	x		x		x	
	Coagulation	x	x		x		x	
	Lipid panel	x	C1 and then every 4 cycles		x			
	Thyroid function	x	C3 and then every 3 cycles					
	Auto-antibody panel	x	In case of suspected Grade ≥ 2 imAEs				In case of suspected imAEs	
	Urinalysis	x	x		x			
	IgE/tryptase						x ^d	x ^d
	Pregnancy test	x (blood test, D -7 to D -1)	C2 and then every 4 weeks (blood or urine)		x (blood or urine)	x ^e (5 months after the last dose)		
Central Laboratory Assessments								
8.5	PK	Refer to Hourly Schedule of Assessments for specific sample collection timepoint details					x	
8.6	ADA							
8.8.1	PD plasma						x	
	PD serum						x	
	PD whole blood flow cytometry						x	
	Whole Blood RNA							
	bTMB/ctDNA							
8.7.1	WGS							
8.8.1	Archival tumor sample							
8.8.2	Fresh tumor biopsy (optional)							
	Tongue scrape (optional)							
	Stool sample (optional)							
8.9	RBR sample (saliva DNA)							

Table 1 Schedule of Activities (cont.)

Abbreviations: ADA = Anti-drug antibody; AE = Adverse event; C = Cycle; D = Day; ECOG = Eastern Cooperative Oncology Group; imAE = Immune-mediated adverse event; IMP = Investigational medicinal product; IRR = Infusion-related reaction; MUGA = Multiple-Gated Acquisition Scans; PD = Pharmacodynamic; PK = Pharmacokinetic; PRO = Patient-reported outcome; RBR = Research biosample repository; TTE = Transthoracic echocardiogram; WGS = Whole genome sequencing.

- a) During the study treatment period, assessments scheduled on the days of study treatment infusions should be performed before the start of infusion unless otherwise noted. Laboratory results have to be available prior the initiation of treatment.
- b) Vital signs include pulse rate, respiratory rate, blood pressure, and temperature at every assessment and blood oxygen saturation pre-dose at visits where tumor assessments are performed. For the first infusion, vital signs should be determined within 60 minutes before and 30 (\pm 10) minutes after the end of infusion. Vital signs will also be collected during the first infusion (every 15 [\pm 5] minutes). During subsequent infusions, vital signs should be determined within 60 minutes before the infusion, during each infusion only as clinically indicated and within 15 (\pm 10) minutes after the end of each infusion. Additional vital signs should be collected during the infusion, if clinically indicated, or if symptoms occurred with the prior infusion. Blood oxygen saturation by pulse oximetry at baseline screening and pre-dose at every visit where tumor assessments are performed.
- c) Participants who discontinue treatment for reasons other than radiographic disease progression per RECIST v1.1 (e.g., toxicity, symptomatic deterioration) will continue scheduled tumor assessments at the frequency described above until radiographic disease progression per RECIST v1.1, initiation of a new anti-cancer therapy, withdrawal of consent, death, or study termination by Sponsor, whichever occurs first. Thus, tumor assessments are to continue according to the schedule in participants who discontinue treatment for reasons other than disease progression or loss of clinical benefit.
- d) Tryptase and total IgE should be analyzed for participants who experience a Grade \geq 3 IRR during the first study treatment administration or for participants who experience a Grade \geq 2 IRR for the first time with the second or subsequent study drug infusion or with clinical signs of hypersensitivity reaction at any time of the conduct of the study. A second sample for IgE/tryptase analysis should be collected at least 48 hours after the onset of the reaction to rule out the possibility of an anaphylactic reaction.
- e) An at-home pregnancy test will be provided. The test has to be conducted 5 months after the final dose (for women of childbearing potential), and the site will inquire about the result during the second follow up.

Table 2 Hourly Schedule of Assessments

	Q2W regimen; Cycle length 14 days	Screening	Cycle 1				Cycle 2			Cycle 3		Cycle 4		Cycle 5				Subsequent Cycles		Treatment Discontinuation
	Day		Day 1				Day 1			Day 1		Day 1		Day 1				Day 1		
	Scheduled Time (h) ^a		PreDose	EOI	4	168	PreDose	EOI	4	PreDose	EOI	PreDose	EOI	PreDose	EOI	4	168	PreDose	EOI	At Visit
Protocol Section	Time Window		-4h	+ 10 min	+/- 1 h	+/- 24 h	-4h	+ 10 min	+/- 1 h	-4h	+ 10 min	-4h	+ 10 min	-4h	+ 10 min	+/- 1 h	+/- 24 h	-4h	+ 10 min	
8.5	PK Sample		x	x	x	x	x	x	x	x	x	x	x	x	x	x	x	x	x	x
8.6	ADA		x				x			x		x		x				C7 and then every 3 cycles		x
8.8.1	PD Serum		x				x			x				x				At the time of tumor assessment		x
	PD Plasma		x				x			x				x				C9 and then every 3 cycles		x
	Whole Blood Flow Cytometry		x			x	x			x				x			x	C9 and then every 3 cycles		x
	Whole Blood RNA		x							x										
	bTMB/ctDNA		x				x			x										
8.7.1	WGS		x																	
8.8.1	Archival Tumor Sample	x																		
8.8.2	Fresh Tumor Biopsy (Optional ^b)	x								x (+2/-1 day[s])										
	Tongue Scrape (Optional ^c)		x (+0/-5 day[s])									x (+0/-5 day[s])								
	Stool Sample (Optional ^c)		x (+0/-5 day[s])									x (+0/-5 day[s])								
8.9	RBR Sample (Saliva DNA) Optional ^d		x																	

Table 2 Hourly Schedule of Assessments (cont.)

Abbreviations: ADA = Anti-drug antibody; C = Cycle; EOI = End of infusion; h = Hour; PD = Pharmacodynamic; PK = Pharmacokinetic; Q2W = Every two weeks; RBR = Research biosample repository; WGS = Whole genome sequencing.

- a) Assessments (e.g., pre-dose) should be performed relative to the start of the study drug infusion except for those at EOI time-points.
- b) As exception, a mandatory baseline fresh biopsy is required to be collected in case no suitable archival tissue sample is available to assess the PD-L1 positivity of a participant's tumor (see Section 5.1)
- c) An additional sample should be taken upon occurrence of colitis, as assessed and confirmed by the Investigator.
- d) Samples for RBR DNA saliva will be collected on Day 1 from all participants who signed RBR ICF prior to study drug infusion. If the RBR DNA saliva sample is not collected during the scheduled visit, it may be collected at any time during the conduct of the clinical study.

Table 3 Schedule of Assessment for Patient-Reported Outcomes

Cycle length 14 days	Day (D)	QLQ-C30 ^a	QLQ-IL97 ^a	QLQ-OES18 ^a	PGI-CI ^a	PGI-S ^a	PRO-CTCAE ^a
Cycle 1	Day 1	x	x	x		x	x
	Day 8 (± 1 day)						x ^b
Cycle 2	Day 1		x	x			x
	Day 8 (± 1 day)						x ^b
Cycle 3	Day 1		x	x	x	x	x
	Day 8 (± 1 day)						x ^b
Cycle 4	Day 1	x		x			x
	Day 8 (± 1 day)						x ^b
Cycle 5	Day 1		x	x			x
	Day 8 ± 1 day)						x ^b
Cycle 6	Day 1		x	x	x	x	x
Cycle 7	Day 1	x		x			x
Cycle 8	Day 1		x	x			x
Cycle 9	Day 1		x	x	x	x	x
Subsequent cycles	Day 1	C10 and then every 6 cycles		x	C12 and then every 6 cycles	C12 and then every 6 cycles	x
Treatment Discontinuation	≤ 30 Days after Last Dose	x		x	x	x	x
Follow-up	90 (±7 days) post last dose, then every 3 months (±2 weeks)	Every 3 months during the 1st year post discontinuation ^b		Every 3 months during the 1st year post discontinuation ^b			At 1st follow-up only ^b

Abbreviations: C = Cycle. PRO = Patient-reported outcome.

- a) All PRO instruments are required to be administered before the participant receives any information on disease status, prior to the performance of non-PRO assessments, and prior to the administration of study treatment, unless otherwise specified. In scenarios where assessments (e.g., blood draws) are done at a different location than the one providing treatment or when they are done on a different day than study treatment administration, laboratory assessments can be completed before the completion of PRO instruments as long as results have not been discussed with participants.
- b) On days where no site visit is planned, remote completion of PROs is accepted.

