8.3 ADVERSE EVENTS AND SERIOUS ADVERSE EVENTS

The definitions of an AE or SAE can be found in [Appendix 2](#). The NSAESI and disease-related events and/or disease-related outcomes not qualifying as AEs or SAEs are discussed in Section [8.3.6](#) and Section [8.3.7](#).

The Investigator and any qualified designees are responsible for ensuring that all AEs (including assessment of seriousness, severity and causality; see [Appendix 2](#)) are

recorded on the Adverse Event eCRF and reported to the Sponsor in accordance with instructions provided in this section and in [Appendix 2](#).

Procedures used for recording AEs are provided in [Appendix 3](#):

8.3.1 Time Period and Frequency for Collecting Adverse Event and Serious Adverse Event Information

The method of recording, evaluating, and assessing causality of AEs and SAEs and the procedures for completing and transmitting SAE reports are provided in [Appendix 2](#).

Investigators will seek information on AEs at each participant's contact. All AEs, whether reported by the participant or noted by study personnel, will be recorded in the participant's medical record and on the Adverse Event eCRF as follows:

After informed consent has been obtained **but prior to initiation of study treatment**, only SAEs caused by a protocol-mandated intervention should be reported (e.g., SAEs related to invasive procedures such as biopsies). Any other AE should not be reported.

After initiation of study treatment, all AEs, regardless of relationship to study treatment, will be reported until 30 days after the final dose of study treatment or until initiation of new systemic anti-cancer therapy, whichever occurs first. SAEs will continue to be reported until 90 days after the final dose of study treatment or until initiation of new systemic anti-cancer therapy, whichever occurs first. In addition, AEs of special interest will continue to be reported until 90 days after the final dose of study treatment, regardless of initiation of new systemic anti-cancer therapy.

Post-study AEs and SAEs: The Investigator is not required to actively monitor participants for AEs after the end of the AE reporting period.

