8.11.3 Assessments at Treatment Discontinuation Visit

Participants who discontinue study treatment early will be asked to return to the clinic ≤ 30 days after the final dose of study drug for a follow-up visit. The visit at which response assessment shows progressive disease may be used as the treatment discontinuation visit.

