4. ABNORMAL LABORATORY VALUES

Not every laboratory abnormality qualifies as an adverse event. A laboratory test result should be reported as an adverse event if it meets any of the following criteria:

- Accompanied by clinical symptoms.
- Results in a change in study treatment (e.g., dosage modification, treatment interruption, or treatment discontinuation).
- Results in a medical intervention (e.g., potassium supplementation for hypokalemia) or a change in concomitant therapy.
- Clinically significant in the Investigator's judgment.

It is the Investigator's responsibility to review all laboratory findings. Medical and scientific judgment should be exercised in deciding whether an isolated laboratory abnormality should be classified as an adverse event.

If a clinically significant laboratory abnormality is a sign of a disease or syndrome (e.g., alkaline phosphatase and bilirubin 5 times the upper limit of normal [ULN] associated with cholecystitis), only the diagnosis (i.e., cholecystitis) should be recorded on the Adverse Event eCRF.

If a clinically significant laboratory abnormality is not a sign of a disease or syndrome, the abnormality itself should be recorded on the Adverse Event eCRF, along with a descriptor indicating if the test result is above or below the normal range (e.g., "elevated potassium", as opposed to "abnormal potassium"). If the laboratory abnormality can be characterized by a precise clinical term per standard definitions, the clinical term should be recorded as the AE. For example, an elevated serum potassium level of 7.0 mEq/L should be recorded as "hyperkalemia."

Observations of the same clinically significant laboratory abnormality from visit to visit should not be repeatedly recorded on the Adverse Event eCRF, unless the etiology changes. The initial severity of the event should be recorded, and the severity or seriousness should be updated any time the event worsens.

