Appendix 4 Clinical Laboratory Tests

The tests detailed in [Table 1](#) will be performed by the local laboratory unless otherwise specified.

Protocol-specific requirements for inclusion or exclusion of participants are detailed in Sections [5.1](#) and [5.2](#), respectively, of the protocol.

Additional tests may be performed at any time during the study as determined necessary by the Investigator or required by local regulations.

Table 1 Protocol-Required Safety Laboratory Assessments

Laboratory Assessments	Parameters
Hematology	
 Leucocytes, erythrocytes, hemoglobin, hematocrit, platelets, differential count (neutrophils, eosinophils, basophils, monocytes, lymphocytes, other cells).
Clinical chemistry	
 Sodium, potassium, chloride, bicarbonate (only required if considered standard of care for the site and in situations where the participant's safety is at risk), glucose, urea or blood urea nitrogen, serum creatinine, protein, serum albumin, phosphate, calcium, total and direct bilirubin, alkaline phosphatase, alanine aminotransferase, aspartate aminotransferase, urate, lactate dehydrogenase, creatine kinase, creatine kinase MB, troponin I and/or troponin T, eGFR determined using the MDRD formula^a, GGT, magnesium, CRP, ferritin.
Coagulation	
 INR or prothrombin time and activated partial prothrombin time; additional coagulation parameters (i.e., antithrombin III [antigenic or chromogenic], fibrinogen, fibrin degradation products, D-dimer) may be assessed according to clinical judgment.
Viral serology	
 HIV, hepatitis B surface antigen (HBsAg), total hepatitis B core antibody (HBcAb), hepatitis C virus (HCV) antibody.
Lipid panel	
 Cholesterol, LDL cholesterol, high-density lipoprotein cholesterol, triglycerides.
Thyroid hormones	
 Free T4, TSH, free T3 (alternatively total T3 if free T3 is not performed)
Quantitative immunoglobulins	
 IgA, IgG, IgM, IgE

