Diarrhea or colitis, Grade 3	
Withhold study drug for up to 12 weeks after event onset. ^aRefer participant to GI specialist for evaluation and confirmatory biopsy.Initiate treatment with 1–2 mg/kg/day IV methylprednisolone or equivalent and convert to 1–2 mg/kg/day oral prednisone or equivalent upon improvement.If event resolves to Grade 1 or better, resume study drug. ^bIf event does not resolve to Grade 1 or better while withholding study drug, permanently discontinue study drug and contact Medical Monitor.
Diarrhea or colitis, Grade 4	
Permanently discontinue study drug and contact Medical Monitor.Refer participant to GI specialist for evaluation and confirmation biopsy.Initiate treatment with 1–2 mg/kg/day IV methylprednisolone or equivalent and convert to 1–2 mg/kg/day oral prednisone or equivalent upon improvement.If event does not improve within 48 hours after initiating corticosteroids, consider adding an immunosuppressive agent.If event resolves to Grade 1 or better, taper corticosteroids over ≥ 1 month.

GI = Gastrointestinal, IV = Intravenous.

- ^a Study Drug may be withheld for a longer period (i.e., > 12 weeks after event onset) to allow for corticosteroids (if initiated) to be reduced to ≤ 10 mg/day oral prednisone or equivalent. The acceptable length of the extended period must be based on the assessment of benefit-risk by the Investigator and in alignment with the protocol requirement for duration of treatment and documented by the Investigator. The Medical Monitor will be available to advise as needed.
- ^b If corticosteroids have been initiated, they must be tapered over ≥ 1 month to ≤ 10 mg/day oral prednisone or equivalent before study drug can be resumed.

ENDOCRINE EVENTS

Thyroid disorders, adrenal insufficiency, diabetes mellitus, and pituitary disorders may be associated with the administration of study drug. Management guidelines for endocrine events are provided in [Table 4](#).

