Participants with unexplained symptoms such as headache, fatigue, myalgias, impotence, constipation, or mental status changes should be investigated for the presence of thyroid, pituitary, or adrenal endocrinopathies. The participant should be referred to an endocrinologist if an endocrinopathy is suspected. Thyroid-stimulating hormone (TSH) and free triiodothyronine and thyroxine levels should be measured to determine whether thyroid abnormalities are present. Pituitary hormone levels and function tests (e.g., TSH, growth hormone, luteinizing hormone, follicle-stimulating hormone, testosterone, prolactin, adrenocorticotrophic hormone levels, and adrenocorticotrophic hormone stimulation test) and magnetic resonance imaging (MRI) of the brain (with detailed pituitary sections) may help to differentiate primary pituitary insufficiency from primary adrenal insufficiency.

Table 4 Management Guidelines for Endocrine Events

Event	Management
Asymptomatic hypothyroidism	
 Continue study drug. Initiate treatment with thyroid replacement hormone. Monitor TSH weekly.
Symptomatic hypothyroidism	
 Withhold study drug. Initiate treatment with thyroid replacement hormone. Monitor TSH weekly. Consider participant referral to endocrinologist. Resume study drug when symptoms are controlled and thyroid function is improving.
Asymptomatic hyperthyroidism	
 TSH ≥ 0.1 mU/L and < 0.5 mU/L: Continue study drug. Monitor TSH every 4 weeks. TSH < 0.1 mU/L: Follow guidelines for symptomatic hyperthyroidism.

Event	Management
Symptomatic hyperthyroidism	
 • Withhold study drug. • Initiate treatment with anti-thyroid drug such as methimazole or carbimazole as needed. • Consider participant referral to endocrinologist. • Resume study drug when symptoms are controlled and thyroid function is improving. • Permanently discontinue study drug and contact Medical Monitor for life-threatening immune-mediated hyperthyroidism.

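### Table 1 schedules no thyroid test at treatment discontinuation, so early stoppers have no scheduled post-baseline test and new asymptomatic dysfunction around stopping can go undetected

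*Combined protocol and SAP*

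**What the plan says.** **Schedule.** In Section 1.3, Table 1, the thyroid row is marked at screening and then reads "C3 and then every 3 cycles". Its Day 8, Treatment Discontinuation, Follow-up and event-triggered cells are empty. Footnote a states that "assessments scheduled on the days of study treatment infusions should be performed before the start of infusion unless otherwise noted", so the Cycle 3 sample precedes the third infusion. The discontinuation visit falls at most 30 days after the last dose.

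**Panel.** Appendix 4 lists thyroid hormones ("Free T4, TSH, free T3 (alternatively total T3 if free T3 is not performed") apart from clinical chemistry, so the chemistry drawn at discontinuation does not include them. Section 8.11.3 adds no test. It does allow an early visit: "The visit at which response assessment shows progressive disease may be used as the treatment discontinuation visit".

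**Risk and action.** Appendix 7 (Endocrine Events) says: "Thyroid disorders, adrenal insufficiency, diabetes mellitus, and pituitary disorders may be associated with the administration of study drug". Its Table 4 has rows for asymptomatic hypothyroidism and hyperthyroidism. For the former one instruction is "Initiate treatment with thyroid replacement hormone", with weekly TSH.

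**Reporting.** Under Appendix 3, Section 4, a laboratory result is an AE if, among other criteria, it "Results in a medical intervention (e.g., potassium supplementation for hypokalemia) or a change in concomitant therapy". Section 8.3.1 says "all AEs, regardless of relationship to study treatment, will be reported until 30 days after the final dose of study treatment"; the sentence goes on to end collection earlier if new systemic anti-cancer therapy starts first.

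**The concern.** Asymptomatic thyroid dysfunction is found only by a laboratory test, and the plan anticipates it closely enough to give management steps for it. Yet the schedule has no thyroid test at the visit where every other cyclically repeated local panel is taken. The earliest stoppers would contribute only a screening value. For most others the last scheduled result predates, or at best coincides with the morning of, the final infusion. Appendix 7 also warns that stopping study drug may not act on an immune-mediated event at once, so the risk does not end with the last dose.

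At stake is a modest piece of safety information: a treatable, reportable abnormality that appears around stopping could be missed and left untreated. Safety against nivolumab is a secondary objective. If thyroid tests are among the laboratory parameters selected for the shift tables in Section 9.3.3, the earliest stoppers would have no scheduled post-baseline value to enter.

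**Working it through.** The documents give no figure on this point to reproduce. The check is a row comparison and calendar arithmetic.

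**1. Row comparison (Table 1, local laboratory).** Seven rows repeat at scheduled treatment cycles: hematology, blood chemistry, coagulation, lipid panel, thyroid function, urinalysis and pregnancy test. Six are marked at Treatment Discontinuation; thyroid function is not. The lipid panel is the closest comparison: it too is periodic (Cycle 1, then every 4 cycles) and it is marked. Not counted are viral serology and immunoglobulins (screening only), and the auto-antibody panel and IgE/tryptase (event-triggered after screening).

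**2. Inputs.** 14-day cycles without delays; Cycle 1 = day 0, so cycle c falls on day 14(c − 1). Thyroid tests are pre-dose at Cycle 3 (day 28), Cycle 6 (day 70), Cycle 9 (day 112) and so on. The discontinuation visit is v days after the last dose, with v from 0 to 30.

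**3. Last dose at Cycle 1 or 2, Cycle 3 work-up not attended.** Scheduled post-baseline thyroid tests: 0. The only result is from screening, 1 to 28 days before Cycle 1. Its age at the discontinuation visit is:
- last dose Cycle 1: from 1 + 0 + 0 = 1 to 28 + 0 + 30 = 58 days;
- last dose Cycle 2: from 1 + 14 + 0 = 15 to 28 + 14 + 30 = 72 days.

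**4. Last dose at Cycle 3 or later.** Stretch from last test to visit = (last dose − last test) + v.

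| Last dose | Test to last dose | v = 7 | v = 14 | v = 30 |
|---|---|---|---|---|
| C3, C6, C9 … | 0 days | 7 | 14 | 30 |
| C4, C7 … | 14 days | 21 | 28 | 44 |
| C5, C8 … | 28 days | 35 | 42 | 58 |

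The exception is a participant who attends a test-cycle work-up (Cycle 3, 6, 9 …) and is then not dosed: that person may have a result after the last dose.

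**5. Benchmark.** The schedule already accepts 3 × 14 = 42 days between on-treatment tests, and 28 + 1 = 29 to 28 + 28 = 56 days from screening to Cycle 3. Comparing the stretches with 42:
- v > 42 cannot occur, since v is at most 30;
- 14 + v > 42 only if v > 28;
- 28 + v > 42 only if v > 14.

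**6. What a test at the visit achieves.** The stretch up to the visit closes to 0, including the 58-day extreme. After the visit, the part of the AE window left without a scheduled test is at most 30 − v days: 23 at v = 7, 16 at v = 14, 0 at v = 30. These are maxima, because AE collection stops earlier if new systemic anti-cancer therapy begins.

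**The case against.** The strongest reply is that this is a design preference. Nothing in the documents requires a thyroid test at discontinuation or conflicts with its absence. Several parts of the reply have force.

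- **The gaps are not remarkable.** Most of the stretches for participants dosed at Cycle 3 or later sit within the accepted 42 days, and the early stoppers' ranges overlap heavily with the accepted screening-to-Cycle-3 interval. A reader might infer from 58 or 72 days that monitoring lapses for an abnormal time. The documents do not support that: 58 needs a visit at day 30 and a last dose two cycles after a test, and 72 needs in addition the earliest possible screening sample. This objection stands.
- **Other routes exist.** Appendix 7 prompts a thyroid work-up for non-specific symptoms such as fatigue or headache, Section 8.11.5 allows unscheduled tests when clinically indicated, and Section 8.3.3.1 follows AEs already recorded. This stands, and confines the point to new, symptom-free dysfunction.
- **Table 4 of Appendix 7 reads as on-treatment guidance.** Its asymptomatic hypothyroidism row opens by continuing study drug. That replacement hormone would also be given after stopping is a reasonable clinical inference, but the protocol does not say so.
- **Omission at discontinuation is not unique.** The auto-antibody row is also unmarked there, and Table 2 repeats whole-blood RNA and bTMB/ctDNA on treatment with no discontinuation sample. So six of seven depends on the stated counting rule. The lipid comparison does not.
- **The cell could be merged in the original table.** Some cells in Table 1 print their text in one row only. This is unlikely here, because the neighbouring marks print row by row and no redaction appears in the thyroid row.

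What survives is the empty cell and its consequence: no scheduled test after stopping.

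**Conclusion.** The point holds as a cheap improvement of minor weight. Participants who stop before the Cycle 3 work-up have no scheduled post-baseline thyroid test. Later stoppers generally have none after their last dose, unless they attend a test-cycle work-up and are not dosed. New asymptomatic dysfunction around stopping can therefore go undetected.

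The day counts assume the nominal 14-day grid; dose delays and the visit window can lengthen them. How many participants are affected cannot be computed, because the documents give neither treatment duration nor a thyroid event rate.

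A reader might go further and infer that thyroid events have been missed, that the arms are compared unfairly, or that the primary analysis is touched. None of these follows. The schedule is the same in every arm, the documents contain no event data, and overall survival does not depend on thyroid testing.

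**What to change.** In Table 1, mark thyroid function (TSH, free T4, and free or total T3, as in Appendix 4) in the Treatment Discontinuation column, using the blood draw already taken at that visit.

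Every participant who attends then has at least one scheduled post-baseline thyroid result; those whose last dose was Cycle 1 or 2 go from none to one. Participants who do not attend gain nothing. When the visit falls early, for instance because the progression visit is used, the test shortens the untested part of the AE window without removing it.

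The cost is one local thyroid panel per attending participant and a one-cell edit, which can wait for the next amendment.
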